Phase 3 registration studies, approximately 60% of subjects achieved durable (>24 weeks) independence from RBC transfusions. The median duration of response was approximately 2 years. Myelosuppression (neutropenia 51-55%; thrombocytopenia 23-44%) was the most frequently reported Grade 3 or 4 toxicity.^{10,31} Phase 2 and Phase 3 studies have also been conducted in transfusion-dependent MDS subjects who did not have the del(5q) abnormality. Rates and durability of transfusion independence (TI) were lower than those observed in the cohorts with the del(5q). Approximately one-quarter of subjects (27%) who received lenalidomide achieved RBC TI, with median duration of response ranging from 33 to 41 weeks.^{39,41} In the placebo controlled Phase 3 study, only 3% of placebo-treated subjects achieved TI lasting at least 8 weeks.

In contrast to lower-risk MDS, poorer OS and more rapid progression to AML that characterizes higher-risk MDS warrant the initiation of disease-modifying therapy. In this setting, 2 hypomethylating agents (azacitidine or decitabine) are used as single agents. The postulated mechanism of action is the reversal of aberrant methylation of tumor suppressor genes that are common in higher-risk MDS.^{26,42} In a Phase 3 study in which decitabine was compared with supportive care, 17% of patients achieved complete remission (CR) or partial remission (PR) according to IWG criteria, and another 13% showed hematologic improvement.²⁷ When azacitidine was evaluated in a randomized study of MDS subjects (higher-risk and lower-risk with significant cytopenias) and compared to supportive care, 14% of subjects achieved CR or PR and an additional 30% showed hematologic improvement based on IWG criteria.⁴⁴

These hypomethylating agents are also used in lower risk MDS patients with multiple cytopenias, frequently after failure of other agents. Low-dose decitabine has been evaluated in 2 Phase 2 studies. In 1 study, decitabine was given at a dose of 20 mg/m² for 3 days per 28-day cycle to 65 subjects with lower risk MDS, of whom 22% achieved an IWG response (per modified IWG 2006).¹⁴ In the other study, decitabine was administered at 3.5 to 7 mg/m² 1-3 times weekly to 25 subjects, of whom 47% achieved an IWG response.³²

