Data from Part 1 of the current study demonstrated activity of imetelstat in subjects with MDS with higher rates of red blood cell (RBC) TI in subjects with non-del(5q).^{11,46} In the initial cohort of 32 MDS subjects, RBC TI was observed in 11 (34%) subjects, with a higher rate of RBC TI in 7 of the 13 (54%) subjects with non-del(5q) MDS and no prior lenalidomide or hypomethylating agent therapy. The study was amended to include only these subjects. As of the clinical cut-off date of 26 October 2018, 38 subjects (13 original and 25 additional) who had non-del(5q) MDS and no prior lenalidomide or hypomethylating agent therapy were enrolled and dosed with imetelstat. The median follow-up for the initial 13 subjects was 29.1 months and 8.7 months for the additional 25 subjects. The median number of treatment cycles was 8 (range, 1-34) and the median dose intensity was 6.9 mg/kg/cycle. The median baseline transfusion burden was 8 units/8 weeks (range, 4-14 units). The 8-week and 24-week were 14/38 (37%) subjects, and 10/38 (26%) subjects, respectively. The median time to onset of RBC TI was 8.1 weeks (range 0.1-33.1 weeks) and the median duration of RBC TI has not been achieved (17 weeks- not estimated [NE]). The mean relative reduction of RBC transfusion burden was 68%, and 8 subjects (21%) had responses by modified IWG 2006 criteria (complete remission [CR]+ marrow CR + partial remission [PR]). The 24-week RBC TI responses were accompanied by a Hb rise of ≥ 3 g/dL. The HI-E rate was 71%.

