4.5.1 Efficacy Analysis Sets

Part 1 (Phase 2):

All Treated analysis set: includes all subjects who receive at least one dose of study drug. This analysis set will be used for all analyses of efficacy endpoints (except time to the 8 or 24-week RBC TI and duration of RBC TI), analyses of disposition, demographics, and baseline disease characteristics.

All Treated 8-week (24-week) TI responder analysis set: includes all treated subjects who do not have any RBC transfusion during any consecutive 8 (24) weeks starting from Study Day 1 until subsequent anti-cancer therapy if any, with the TI starting date between Study Day 1 and date of last dose of study medication + 30 days or End of Treatment Visit whichever occurs first. This analysis set will be used for analyses for time to RBC TI and duration of RBC TI.

Part 2 (Phase 3):

Intent-to-Treat (ITT) analysis set: includes all subjects randomized into the main study. This analysis set will be used for all analyses of efficacy and patient-reported outcomes (PRO) endpoints (except time to the 8 or 24-week RBC TI and duration of RBC TI), analyses of disposition, demographic, and baseline disease characteristics. Subjects will be classified according to assigned treatment group, regardless of the actual treatment received.

ITT 8-week (24-week) TI responder analysis set: includes all subjects in the ITT analysis set who do not have any RBC transfusion during any consecutive 8 (24) weeks starting from Study Day 1 until subsequent anti-cancer therapy if any, with the TI starting date between Study Day 1 and date of last dose of study medication + 30 days or End of Treatment Visit whichever occurs first. This analysis set will be used for analyses for time to the RBC TI and duration of RBC TI.

Modified ITT (MITT) analysis set: includes all ITT subjects who received at least one dose of study drug according to assigned treatment group. This analysis set will be used for sensitivity analyses for 8-week and 24-week RBC TI in the case there are subjects who were dosed, but didn't receive the assigned treatment.

Per-protocol (PP) analysis set: This analysis set is a subset of the ITT analysis set. Subjects with key protocol deviations will be excluded from the PP analysis set. The categories and terms of the key protocol deviations leading to exclusion are defined in the project-specific Protocol Deviation Specification.

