4.9 Efficacy Evaluation

4.9.1 Analysis and Data Conventions

Unless otherwise specified, all statistical tests will be interpreted at a 2-sided nominal significance level of 0.05 and all CIs at a 2-sided level of 95%. The overall type I error rate is 0.05 (two-sided) for the primary and secondary efficacy hypotheses in each part of the study.

Statistical Hypotheses for Trial Objectives

For Part 1 (Phase 2), RBC TI in 5 or more of 30 subjects rejects null rate of 6.5% with a single-arm, one-sided, level 0.05 exact test.

For Part 2 (Phase 3), the primary hypothesis of this study is that the imetelstat will significantly improve the rate of RBC TI as compared to placebo in transfusion dependent subjects with low or intermediate-1 risk MDS that is relapsed or refractory to ESA treatment.

The statistical hypotheses are as follows:

H₀: The RBC TI rate of experimental treatment group and the placebo group are equal.
H₁: The RBC TI rate of experimental treatment group is greater than the placebo group.

The hypothesis will be tested using a stratified Cochran-Mantel-Haenszel (CMH) test adjusting for the stratification factors at a two-sided significant level of 0.05.

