4.9.1.3 Multiple Comparisons/Multiplicity

Testing of Primary Endpoint for Part 2 (Phase 3)

For Part 2, the primary hypothesis is that imetelstat will increase the rate of RBC TI as compared to placebo in transfusion dependent subjects with low or intermediate-1 risk MDS that is relapsed/refractory to ESA treatment. The primary efficacy hypothesis on 8-week RBC TI will be tested at 0.05 (two-sided) for Part 2.

Testing of Secondary Endpoints for Part 2 (Phase 3)

For Part 2, a sequential gate-keeping procedure and Hochberg procedure will be implemented to ensure that the overall type I error rate for the secondary endpoints is controlled. Let α be the critical type I error rate 0.05 (2-sided). 24-week RBC TI and rate of HI-E per modified IWG 2006 are the most important secondary endpoints, thus will be used as gate keepers and be tested at the α level sequentially. 24-week RBC TI will be the first gate keeper and rate of HI-E per modified IWG 2006 will be the second gate keeper. If the nominal p-value is $< \alpha$ for 24-week TI, then rate of HI-E will be tested next at the α level. If the nominal p-value is $< \alpha$ for rate of HI-E as well, the remaining selected secondary hypotheses (PFS, and OS) will be tested using a Hochberg procedure [2].

In summary, the secondary endpoints as the gate keepers which will be tested sequentially at 0.05 (2-sided) are:

1. 24-week RBC TI
2. Rate of HI-E per modified IWG 2006

If the above two gate keepers are significant, the following endpoints will be tested using a Hochberg procedure:

- PFS
- OS

In general, Hochberg procedure is conducted as the following steps:

1. Suppose we have H_1, \dots, H_m null hypotheses tested and P_1, \dots, P_m as their corresponding p-values. We order these p-values in increasing order and denote them by $P_{(1)}, \dots, P_{(m)}$.
2. For a given significance level α , find the largest k such that $P_{(k)} \leq \alpha / (m+1-k)$.
3. Reject the null hypothesis for all $H_{(i)}$ for $i=1, \dots, k$.

Note that Hochberg procedure does not require the order of hypotheses and it controls the overall type I error when conducting multiple comparisons at the given significance level α if the p-values are independent or positively correlated.

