4.9.3.2 Analysis Methods

Part 1 (Phase 2):

The proportion of subjects with 24-week RBC TI, CR, PR, and hematologic improvement, and other binary endpoints, will be summarized with percentage along with its 95% 2-sided exact Clopper-Pearson CI. The time to 8-week RBC TI and time to 24-week RBC TI will be summarized descriptively based on 8-week and 24-week TI responder analysis set, respectively. The Kaplan-Meier method will be used to estimate the distribution of duration of RBC TI based on 8-week and 24-week TI responder analysis set, respectively. The distribution of OS, PFS, and time to progression to AML will be summarized using similar Kaplan-Meier methods.

Part 2 (Phase 3):

The 24-week RBC TI rates will be summarized with frequencies and percentages along with 2-sided 95% exact Clopper-Pearson CIs for the 2 treatment groups. Difference in TI and its 95% CI will be presented using Wilson Score method [1]. The comparison will be based on a stratified CMH test adjusting for the stratification factors at a two-sided significant level of 0.05.

Sensitivity analyses will be performed for Part 2 to evaluate the robustness of the 24-week RBC TI endpoint and includes:

- CMH test of 24-week RBC TI based on MITT analysis set in the case there are subjects who were dosed, but didn't receive any assigned treatment;
- CMH test of 24-week RBC TI based on per-protocol analysis set;

The time to 8-week and 24-week RBC TI will be summarized descriptively for the 2 treatment groups based on ITT 8-week and 24-week TI responder analysis set, respectively. The Kaplan-Meier method will be used to estimate the distribution of duration of RBC TI based on ITT 8-week and 24-week TI responder analysis set, respectively, and will be compared between two treatment groups using stratified log rank test based on ITT 8-week responder analysis set. The distribution of cumulative duration of RBC TI ≥ 8 weeks (sum of all durations of RBC TI ≥ 8 weeks) will be estimated by Kaplan-Meier based on ITT 8-week responder analysis set as well.

The proportion of subjects with hematologic improvement, CR, PR, or mCR per modified IWG 2006, and other binary endpoints will be evaluated using the same statistical methods as for the endpoint of 24-week RBC TI rates. The 8-week RBC TI rate in the first 24 weeks and 48 weeks (proportion of subjects who had RBC TI ≥ 8 weeks in the first 24/48 weeks) will be evaluated similarly.

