4.12 Determination of Sample Size

Approximately 270 subjects (57 subjects already enrolled in Part 1, approximately 170 subjects in the main study of Part 2, and approximately 45 subjects in Ventricular Repolarization substudy of Part 2) will be enrolled in the study.

On the basis of historical data, RBC TI rate is expected to be approximately 7.5% [15, 16] in subjects with low or intermediate-1 risk MDS without any active treatment. The RBC TI rate with imetelstat treatment is expected to be approximately 30% based on preliminary data from [17]. The futility criteria before Amendment 2 were defined as follows: If 4 or fewer subjects among 30 subjects in Part 1 achieve RBC TI lasting at least 8 weeks, the study will be stopped unless there is compelling clinical evidence of efficacy in one or more other endpoints (eg, transfusion reduction, erythroid improvement). The initial cohort of 32 subjects enrolled into Part 1 was expanded with Amendment 2 to include an additional 25 subjects with non-del(5q) MDS and without prior exposure to either hypomethylating agents or lenalidomide who meet the revised entrance criteria, for a total of 57 subjects in Part 1.

Since data from Part 1 for this target population show clinical benefit of treatment with imetelstat, Part 2 of the study will be initiated. If the RBC TI rate of 30% with imetelstat treatment is true, the probability of passing the futility criterion is 97%. All available data will be used to support the decision.

In the main study of Part 2, approximately 170 subjects will be randomized in a 2:1 ratio to receive either imetelstat or placebo the main study of Part 2. Using a 2:1 ratio randomization and a 2-group continuity corrected Chi square test with 0.05 (2-sided) significance level, 150 subjects are needed to achieve a power of approximately 88% to detect the difference between an RBC TI rate of 30% in the imetelstat group and an RBC TI rate of 7.5% in the placebo group. After correction for a 10% drop-out rate, a total of approximately 170 subjects (115 in imetelstat group and 55 in placebo group) will be needed. The overall study power from Part 1 and the main study of Part 2 is approximately 85%.

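### The between-arm log-rank test of duration of RBC TI is run in 8-week responders only: its p-value is not a randomised comparison and should be labelled descriptive or dropped

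*SAP*

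**What the plan says.** SAP 4.9.3.2 (Part 2) estimates duration of RBC TI by Kaplan-Meier in the 8-week and 24-week responder sets. It then says that duration will be estimated "and will be compared between two treatment groups using stratified log rank test based on ITT 8-week responder analysis set".

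That set, in SAP 4.5.1, "includes all subjects in the ITT analysis set who do not have any RBC transfusion during any consecutive 8 (24) weeks", subject to rules on start date and later anti-cancer therapy.

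The neighbouring responder analyses carry no test. "The time to 8-week and 24-week RBC TI will be summarized descriptively for the 2 treatment groups", and cumulative duration of TI is only estimated by Kaplan-Meier.

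SAP 4.9.1 sets the default reading: unless otherwise specified, "all statistical tests will be interpreted at a 2-sided nominal significance level of 0.05". Neither document labels the duration p-value descriptive or notes that responders are not randomised groups.

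SAP 4.9.1.3 lists the secondary endpoints under error control: "24-week RBC TI will be the first gate keeper", followed by HI-E and then PFS and OS by Hochberg. Duration is not listed.

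Protocol 11.4 plans only Kaplan-Meier estimation of duration in responders. Protocol 3.2 (Randomization and Treatment Groups) does, however, include comparing duration of TI between the arms among the Part 2 efficacy objectives.

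**The concern.** There are two separate problems.

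**Interpretation.** Randomisation makes the 170 subjects comparable, not the subset who respond. If imetelstat turns some subjects into responders who would not have responded on placebo, the imetelstat responders mix natural and drug-induced responders, while the placebo responders are natural only. A difference in duration may then reflect who entered each group. More placebo responders would not cure this.

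**Calibration.** The asymptotic log-rank test relies on an approximately normal statistic. With about four placebo responders over four strata, the statistic is skewed. The placebo event count can fall only a little below its small expectation but can rise well above it, and a placebo excess is the direction that favours imetelstat.

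At stake is how one secondary p-value is reported. Read at 0.05, it would appear beside the median durations as evidence that responses last longer on imetelstat, which this comparison cannot establish.

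**Working it through.** **The plan's own figures.** SAP 4.12 plans on "an RBC TI rate of 30% in the imetelstat group and an RBC TI rate of 7.5% in the placebo group". With 100 and 50 evaluable subjects and a continuity-corrected two-sided 0.05 test, power is 87.6% (stated: about 88%). 150/(1 − 0.10) = 167 (stated: about 170). The chance of passing the Part 1 futility rule at a true 30% is 97.0%, and 0.970 × 0.876 = 85.0% (stated: about 85%). All reproduce, so the planning rates are used as they stand.

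**Size of the tested set.**
- Imetelstat: 115 × 0.30 = 34.5 responders.
- Placebo: 55 × 0.075 = 4.125, which is 4.125/38.625 = 10.7% of responders and about one per stratum.
- Placebo responders ~ Binomial(55, 0.075): P(3 or fewer) = 0.401.
- Protocol 1.1.4 reports that, in a placebo-controlled Phase 3 lenalidomide study, "only 3% of placebo-treated subjects achieved TI lasting at least 8 weeks". At 3%, 55 × 0.03 = 1.65 are expected and P(none) = 0.187, in which case no test is possible.

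**A duration scale.** Protocol 1.1.5 reports for Part 1: "The 8-week and 24-week were 14/38 (37%) subjects, and 10/38 (26%) subjects, respectively". So 10 of 14 eight-week responders reached 24 weeks, 16 weeks later. If durations beyond week 8 are exponential, exp(−16λ) = 10/14, so λ = ln(1.4)/16 = 0.0210 per week and the median is ln 2/λ = 33 weeks. The exact 95% interval for 10/14 (0.419 to 0.916) gives medians of 13 to 127 weeks. The 33 weeks may be short: the same section reports the median duration as not reached.

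**Level when durations are identical.** The statistic is Z = Σ(O − E)/√ΣV over strata, judged against ±1.96. Simulation: 20,000 trials per setting, 115 and 55 subjects, 30% and 7.5% responders, the same exponential durations in both arms. Four equal strata and censoring uniform over 30 to 110 weeks are assumptions.

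| Median (weeks) | Imetelstat longer | Imetelstat shorter | Two-sided |
|---|---|---|---|
| 13 | 5.9% | 1.5% | 7.4% |
| 24 | 6.2% | 1.4% | 7.6% |
| 33 | 5.7% | 1.4% | 7.1% |
| 60 | 5.8% | 0.9% | 6.7% |
| 127 | 5.4% | 0.3% | 5.7% |

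Nominal is 2.5% each way. A separate run at 33 weeks gave 5.8% and 1.3%. Variations at 33 weeks (longer/shorter):
- strata of 30/30/20/20%: 6.0%/1.3%
- censoring over 10 to 60 weeks: 5.8%/0.7%
- censoring over 50 to 150 weeks: 6.1%/1.5%
- no stratification: 7.0%/1.0%
- placebo rate 3%: 7.6%/0.5%, with 19% of trials untestable

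**Ability to detect a real difference.** Schoenfeld, if all 38.6 responders had events: d·a(1 − a) = 38.625 × 0.107 × 0.893 = 3.68, with square root 1.92. At HR 0.5, power = Φ(0.693 × 1.92 − 1.96) = 26%. For 80% power the HR must be about exp(−2.80/1.92) = 0.23.

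**Illustration of the interpretation problem.** Suppose the drug only adds responders and leaves natural responders' durations unchanged. In simulations with assumed hazards (unstratified), the test rejected in 11% of trials when the added responders had twice the hazard, with the drift against imetelstat. It rejected in 21% when they had half the hazard, with the drift in favour. This shows that the problem can act in either direction. It does not estimate its size here, because the documents give no placebo TI durations.

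**The case against.** **Error control is untouched.** Duration is outside the family in SAP 4.9.1.3, SAP 4.9.1 calls its default level nominal, and durable response is already tested in all randomised subjects through 24-week RBC TI. This stands. A reader might infer that the duration test inflates the trial's overall type I error; the documents do not support that, because no listed endpoint depends on it.

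**The protocol wants a comparison.** A reader might infer that the SAP contradicts Protocol 11.4 by adding a test. It does not. Protocol 3.2 names comparing duration as an objective, and Protocol 11 leaves details to the SAP. Likewise, the fact that time to TI gets no test does not by itself make the duration test the anomaly, since Protocol 3.2 names that comparison too.

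**The miscalibration is small.** At the planned placebo rate the two-sided level is about 6 to 7% at most medians, and lowest (5.7%) at the long durations that Part 1 makes plausible. This also stands, although the tilt towards imetelstat persists in every setting tried.

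**A non-significant result is not empty.** Power is low for moderate differences, but with no placebo durations in the documents a very large one cannot be excluded.

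**A better-calibrated test could be used.** This does not rescue the comparison. A within-stratum permutation test based on |Z| gave 3.6%/0.7%, and only an equal-tailed version came near balance (about 1.9%/1.7%). Neither makes responders a randomised comparison.

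**Conclusion.** The point holds, at modest size. The certain part needs no simulation: the set is formed after randomisation by a treatment-affected outcome, so the p-value does not test a treatment effect on duration, and nothing in the SAP says so. The miscalibration is secondary: a two-sided level of about 6 to 7% (5.7 to 7.6% across the medians tried), with the whole excess favouring imetelstat. It rests on the planning rates, exponential durations, equal strata and uniform censoring that is the same in both arms.

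The consequence is limited to one nominal secondary p-value. The primary analysis, the gatekept endpoints and the sample size are unaffected.

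**What to change.** In SAP 4.9.3.2 keep the Kaplan-Meier estimates of duration by arm in responders, and do one of two things:

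- delete the log-rank comparison, which leaves what Protocol 11.4 plans; or
- keep it and add: *Any between-arm p-value for duration of RBC TI in responders is descriptive, is not a randomised comparison, and is not interpreted at the 0.05 level of Section 4.9.1.*

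In either case, add a sentence naming the planned ITT 24-week RBC TI test as the randomised comparison of durable response, and noting that it combines achieving and keeping TI and so does not test duration alone. Do not substitute a recalibrated test.

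Cost: one or two SAP sentences, with no change to sample size, alpha or data collection. The p-value beside the median durations is lost or loses weight, and the duration objective in Protocol 3.2 is met descriptively only.

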4.9.2 Primary Efficacy Variable – 8-week rate of RBC TI

4.9.2.1 Variable Definition

The primary variable for the assessment of efficacy is the rate of RBC TI lasting at least 8 weeks. The 8-week RBC TI rate is defined as the proportion of subjects without any RBC transfusion

during any consecutive 8 weeks (56 days) starting from Study Day 1 until subsequent anti-cancer therapy if any. The starting date of 8-week RBC TI duration must be between Study Day 1 and the date of last dose of study drug + 30 days or End of Treatment Visit whichever occurs first, or Study Day 31 if randomized but not treated.

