4.9.2.2 Analysis Methods

The primary efficacy analysis is planned at 12 months after the last subject is randomized in the main study of Part 2, and the final analysis is at the End of the Study defined as 24 months after randomization of the last subject in the main study of Part 2 or anytime the sponsor terminates the study, whichever comes first.

Efficacy data in Part 1 will be descriptively summarized based on the treated population. Efficacy data the main study of in Part 2 will be compared between the imetelstat and placebo groups based on the ITT population. Any available efficacy data from Ventricular Repolarization Substudy will be descriptively summarized in addition to the efficacy data from the main study in Part 2.

Part 1 (Phase 2):

The proportion of subjects with 8-week RBC TI will be summarized with a frequency and percentage along with its 95% 2-sided exact Clopper-Pearson CI. The forest plot of the subgroup (defined in section 4.9.1.4) corresponding rate and associated 2-sided 95% CIs will be presented.

Part 2 (Phase 3):

The 8-week RBC TI rates will be summarized with frequencies and percentages along with 2-sided 95% exact Clopper-Pearson CIs for the 2 treatment groups. Difference in TI and its 95% CI will be presented using Wilson Score method [1]. The comparison will be based on a stratified CMH test adjusting for the stratification factors at a two-sided significance level of 0.05:

1. Prior RBC transfusion burden (≤ 6 or > 6 units RBC)
2. IPSS risk group (low risk or intermediate-1 risk)

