4.9.3 Key Secondary Efficacy Variables

4.9.3.1 Variables Definition

24-week RBC TI rate

24-week RBC TI rate is defined as the proportion of subjects without any RBC transfusion during any consecutive 24 weeks (168 days) starting from Study Day 1 until subsequent anti-cancer therapy if any. The starting date of 24-week RBC TI must be between Study Day 1 and the date of last dose of study drug + 30 days or End of Treatment Visit whichever occurs first, or Study Day 31 if randomized but not treated.

Time to 8-week (24-week) RBC TI

Time to 8-week (24-week) RBC TI is defined as the interval from Study Day 1 to the first day of the first 8-week (24-week) RBC TI period.

Duration of RBC TI

Duration of RBC TI is defined as the first day of the longest RBC TI period to the date of the first RBC transfusion after the TI period starts. Subjects who have not had an RBC transfusion ending the TI period at the time of analysis or who withdraw from the study will be censored at the date of the last transfusion evaluation or the day before the first date of subsequent anticancer therapy if given, whichever occurs first.

Rate of hematologic improvement, including HI-E, per modified IWG 2006

The modified IWG 2006 criteria [5] for HI define specific responses of cytopenia in the three hematopoietic lineages: erythroid (HI-E), platelet (HI-P), and neutrophil (HI-N). Rate of hematologic improvement is defined as the proportion of subjects who achieve HI-E, or HI-P, or HI-N.

HI-E is defined as a hemoglobin (Hb) increase of at least 1.5 g/dL above pretreatment and lasts at least 8 weeks or reduction of at least 4 units of RBC transfusion units/8 weeks compared with the prior RBC transfusion burden. A valid 8-week period must start before the date of last dose of study drug + 30 days or End of Treatment Visit whichever occurs first, or Study Day 31 if randomized but not treated, and ends before the first transfusion in posttreatment follow-up or the first day of subsequent anti-cancer therapy whichever occurs first. Pretreatment Hb level is defined as the average of all the Hb values (from transfusion history, local, and central lab) in the 8 weeks prior to first dose date, including the value on first dose date (Part 1 or Part 2) and excluding values that were within 14 days after transfusion (thus considered to be influenced by transfusion) for all

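### A closed longest TI period counts as a Kaplan-Meier event even while a later TI period is running, so duration of RBC TI is somewhat understated; cumulative TI has no event or censoring rule

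*SAP*

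**What the plan says.** **Duration.** SAP 4.9.3.1: "Duration of RBC TI is defined as the first day of the longest RBC TI period to the date of the first RBC transfusion" once that period has begun. On censoring: "Subjects who have not had an RBC transfusion ending the TI period at the time of analysis or who withdraw from the study will be" treated as censored at the last transfusion evaluation, or the day before subsequent anticancer therapy if that is earlier. Protocol 9.2.2 uses the same longest-period definition.

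**Analysis.** SAP 4.9.3.2 estimates this duration by Kaplan-Meier in 8-week and 24-week responders. It "will be compared between two treatment groups using stratified log rank test based on ITT 8-week responder analysis set".

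**Cumulative duration.** The same section adds the total of a subject's TI periods of at least 8 weeks, whose distribution "will be estimated by Kaplan-Meier based on ITT 8-week responder analysis set as well". It does not say what counts as an event, when a subject is censored, or on what time scale.

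**When a period may start.** Under SAP 4.9.2.1 the start of a TI period "must be between Study Day 1 and the date of last dose of study drug + 30 days" or the End of Treatment visit, whichever is first. Protocol 9.3.1.1 stops posttreatment transfusion collection at the first transfusion in follow-up.

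**Timing.** SAP 4.9.2.2: "The primary efficacy analysis is planned at 12 months after the last subject is randomized in the main study of Part 2", with a final analysis at 24 months.

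**Status.** Duration of RBC TI is a secondary objective and endpoint (SAP 2.2, 3.2.2). It is not in the testing sequence of SAP 4.9.1.3, which covers 24-week TI, HI-E, PFS and OS.

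**The concern.** Kaplan-Meier needs a time that closes at a definite event. The longest TI period is chosen after the fact, and the choice can change for as long as another period is running or can still start. Under SAP 4.9.3.1, once a transfusion has ended the period that is currently longest, the subject is an event at that length, even if a later period is running and may overtake it. What is known at that moment is a lower bound, which calls for censoring.

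Repeat periods are not foreign to the plan: summing all durations of at least 8 weeks presupposes them. The medians will be read as the durability of the response, and a between-arm log-rank test is planned on the same quantity.

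**Working it through.** The plan gives no expected value for TI duration or cumulative TI, so there is no planned figure to reproduce. The check is of the rule itself, and then of its possible size under stated assumptions.

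**1. The rule applied to one subject.** At the cutoff a treated responder has a closed 10-week TI period and a second one that has run 9 weeks.
- SAP 4.9.3.1: the longest period is the 10-week one and a transfusion ended it, so event at 10 weeks.
- What is known: longest period at least 10 weeks; sum at least 10 + 9 = 19 weeks.

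**2. Who is affected.** No period may start after last dose + 30 days or the End of Treatment visit. Both quantities are therefore final once the last eligible period has closed. Only subjects still on treatment, within that start window, or in a running TI period at the cutoff can be misclassified.

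**3. Size for the longest period.** Assumptions, none from the documents: TI periods of 8 weeks plus an exponential with mean 30 weeks, gaps with mean 10 weeks, follow-up of 40 to 110 weeks, exponential treatment time, new periods starting only on treatment. Medians in weeks:

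| Mean treatment | Regain TI after each loss | Complete follow-up | SAP rule | Shortfall |
|---|---|---|---|---|
| 32 | 30% | 31.1 | 30.9 | 0.2 |
| 32 | 50% | 32.5 | 31.9 | 0.6 |
| 32 | 70% | 34.8 | 33.7 | 1.1 |
| 60 | 30% | 32.2 | 31.5 | 0.7 |
| 60 | 50% | 34.8 | 33.2 | 1.6 |
| 60 | 70% | 37.3 | 34.5 | 2.8 |

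Repeat runs of the first row give 0.2 to 0.3. With mean treatment of 100 weeks and 70% regaining, the shortfall is about 5 weeks. With nobody regaining TI it is zero.

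**4. A second model.** Uniform entry over 104 weeks, cutoff 52 or 104 weeks after last entry, exponential TI periods, gaps and treatment time. Longest-period medians, complete follow-up against SAP rule:

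| Setting | 12-month cutoff | 24-month cutoff |
|---|---|---|
| Every loss on treatment can be followed by a new period, mean treatment 60 weeks | 42.9 vs 38.8 (4.1 short) | 43.1 vs 41.7 (1.4) |
| Same, mean treatment 100 weeks | 50.1 vs 41.0 (9.1 short) | 50.2 vs 45.8 (4.4) |
| 60% have no further TI after each period, mean treatment 60 weeks | 39.8 vs 38.9 (0.9 short) | 40.1 vs 40.0 (0.1) |
| One period only | 42.5 vs 42.5 | 42.2 vs 42.2 |

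The first two rows let everyone regain TI while treated, so they lie outside the 30 to 70% range and serve as an outer bound.

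**5. Does a different censoring rule repair it?** In the 60-week setting of step 3, censoring whenever any TI period is running gives 32.3, 34.9 and 37.5 weeks against 32.2, 34.8 and 37.3. Kaplan-Meier on the first qualifying period is unbiased.

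**6. The cumulative sum.** Second model, 12-month cutoff, medians in weeks:

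| Setting | Complete follow-up | Out of TI at cutoff = event | Censored unless final |
|---|---|---|---|
| Every loss can be followed by a new period, mean treatment 60 | 56.5 | 51.5 | 56.3 |
| 60% have no further TI | 42.6 | 41.9 | 50.1 |
| One period only | 42.5 | 42.5 | 53.0 |

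Neither obvious rule is safe in every setting, so leaving the rule unstated matters.

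**The case against.** **The effect may be small.** This stands. At the planned rates there would be about 0.30 × 115 = 34.5 imetelstat and 0.075 × 55 = 4.1 placebo responders. Sampling error in the medians, and above all in the between-arm comparison, will outweigh a shortfall of a week or two. The 24-month analysis reduces it further, and the planned swimmer-lane plots may let a reader see repeat periods.

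**The longest period is the protocol's own definition.** This also stands: replacing it by the first period would be a preference. The defect lies in the censoring rule, which can be changed without touching the definition.

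**Stronger readings that a reader might infer, and that the documents do not support:**
- That the SAP scores the cumulative sum as an event when a period ends. It states no rule for the sum; the criticism is that the rule is missing.
- That neither quantity is final while a subject is followed. The start window closes at last dose + 30 days or the End of Treatment visit.
- That cumulative medians could be wrong by some 28 weeks. With no treatment stop and 70% regaining, a simulation gives 61.8 against 90.1 weeks, but the second figure counts periods that the SAP would not. With treatment stopping at a mean of 60 weeks and otherwise the same inputs it is 45.4 against 46.9.
- That the arms are biased differently. The documents give no rate of regaining TI in either arm.

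**Conclusion.** The point holds for the longest period as written: a closed longest period is an event even when a running period may overtake it, and this pushes reported duration downward. Under the assumed 30 to 70% regaining TI and mean treatment of 32 to 100 weeks, the median is about 0.3 to 5 weeks short at the earlier cutoff. The shortfall is zero without repeat periods and smaller at 24 months. These are illustrations: the documents give no frequency of repeat TI, so no size can be stated for this trial.

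For cumulative TI the finding is a missing event and censoring rule, with the same bias if being out of TI at the cutoff is scored as an event.

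The duration medians and the responder-only log-rank test are affected. The primary test, the sample size and the gate-keeping and Hochberg sequence are not. The change is worth making before the analysis because it is cheap and the medians will be quoted as durability.

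**What to change.** 1. **Duration of RBC TI (SAP 4.9.3.1).** Keep the longest-period definition. Add that a subject with any TI period running at the cutoff is censored at the longest length observed so far. Say whether a transfusion-free interval that has not yet reached 56 days counts as running. Counting only those that have reached it fits the TI definition, but leaves a small part of the shortfall in place.
2. **Supportive analysis (SAP 4.9.3.2).** Add Kaplan-Meier of the first qualifying TI period, the period that time to TI already uses.
3. **Cumulative TI (SAP 4.9.3.2).** Replace the Kaplan-Meier curve with a descriptive summary by arm of total days in TI periods of at least 56 days within the first 48 weeks, in 8-week responders. Every subject has at least 48 weeks of potential follow-up at the 12-month cutoff, and the SAP already uses a 48-week window for 8-week TI. State the rules for death, withdrawal, subsequent therapy and periods crossing week 48. An all-ITT version is optional and should be labelled as mixing response rate with durability. Add no formal test.

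**Cost.** SAP wording and slightly more programming on data already collected, and a somewhat higher share of censored durations. The 48-week total says nothing about later durability, which stays with the Kaplan-Meier analyses in items 1 and 2.
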